9.4. Variables

9.4.1. Exposure ascertainment

Exposure to IV pantoprazole will be identified from inpatient procedure and drug codes including any of the following NDC and HCPCS codes shown in Table 2. Only the first treatment episode during the study period will be of interest.

Version 2.0, 10 February 2022

Table 2. NDC and HCPCS Codes indicating IV administration of pantoprazole			
Code	Description		
NDC			
0008-0941-01	40 mg/vial pantoprazole		
0008-0941-02	40 mg/vial pantoprazole (10 vials)		
0008-0941-03	40 mg/vial pantoprazole (25 vials)		
0008-2001-01	40 mg/vial pantoprazole Single vial		
0008-2001-10	40 mg/vial pantoprazole 10 vials		
0008-2001-25	40 mg/vial pantoprazole 25 vials		
0008-4001-01	40 mg/vial pantoprazole Single vial		
0008-4001-10	40 mg/vial pantoprazole 10 vials		
0008-4001-25	40 mg/vial pantoprazole 25 vials		
0008-0923-51	40 mg/vial pantoprazole Single vial		
0008-0923-55	40 mg/vial pantoprazole 10 vials		
0008-0923-60	40 mg/vial pantoprazole 25 vials)		
HCPCS			
S0164	Injection pantoprazole sodium, 40 mg		
C9113	Injection, pantoprazole sodium, per vial		

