Variables Exposure to IV pantoprazole will be identified from inpatient procedure and drug codes including National Drug Codes (NDC) and Healthcare Common Procedure Coding System (HCPCS) codes. The date of first administration of IV pantoprazole will be defined as the index date. For each outcome, patients will be followed from the index date to whichever of the following occurs first: occurrence of the outcome of interest, 90 days following the last date of IV pantoprazole administration, initiation of a separate IV pantoprazole infusion within 90 days following the discontinuation of IV pantoprazole administration, death, end of enrollment in the database, or end of study period (ie, 31 December 2020). The following outcomes of interest will be defined based on the presence of at least one ICD-9-CM or ICD-10-CM diagnosis code identified in the inpatient or outpatient setting during the follow-up period:

- Agranulocytosis
- Thrombocytopenia
- Leukopenia

- Pancytopenia
- Hypersensitivity (including anaphylactic reactions and anaphylactic shock)
- Hyperlipidaemia
- Hypertriglyceridemia
- Hyponatraemia
- Hypomagnesaemia
- Hypocalcaemia
- Hypokalaemia
- Diarrhea
- Vomiting
- Abdominal distension
- Hepatobiliary injury
- Urticaria
- Angioedema
- Stevens-Johnson syndrome
- Lyell syndrome
- Erythema multiforme
- Drug Rash with Eosinophilia and Systemic Symptoms (DRESS)
- Tubulointerstitial nephritis
- Photosensitivity
- Peripheral edema and
- Injection site thrombophlebitis

The other key variables of interest to be collected include demographic characteristics, comorbidities, and duration and dose of IV pantoprazole.

Data sources

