9. RESEARCH METHODS

9.1. Study design

This will be a retrospective cohort study with no comparator group. No a priori hypotheses are specified. Descriptive analyses including an estimation of incidence rates will be performed.

9.2. **Setting**

The study will be conducted using Optum's longitudinal integrated EHR from the US¹, which is described in Section 9.5 This data source includes data from adjudicated administrative insurance claims, inpatient electronic health records, as well as outpatient EHR enabling capture of exposure to IV pantoprazole in the study population of interest. The study period will be defined from 01 January 2007 to 31 December 2020.

9.3. **Study population**

Two separate cohorts, ie, infants aged 1 month to <1 year and patients aged 1 to <2 years will be identified during the study period using the following inclusion and exclusion criteria.

9.3.1. **Inclusion criteria**

Patients must meet all of the following inclusion criteria to be eligible for inclusion in the study:

- 1. At least one administration of IV pantoprazole during the study period from January 1, 2007 to December 31, 2020, and
- 2. For the cohort of infants aged 1 month to <1 year (Cohort 1): Age 1 month to <1 year on the index date (ie, the date of first administration of IV pantoprazole); For the cohort of patients aged 1 to <2 years (Cohort 2): Age 1 to <2 years on the index date.
- 3. Patients must be enrolled in the database for at least 30 days prior to the index date

In addition to this 30-day lookback window, patients will be further excluded based on the occurrence of a history of outcomes of interest identified in Table 3 occurring prior to the index date.

9.3.2. **Exclusion criteria**

Patients meeting any of the following criteria will not be included in the study:

1. Patients with any of the following ICD-9-CM or ICD-10-CM codes occurring prior to or on the index date indicating a preterm birth or birth weight less than 2.36 kilograms will be excluded:

ICD-9-CM codes: 765.01-765.08; 765.10-765.19; 765.21-765.28

ICD-10-CM codes: P07.21-P07.26; P030-P039; P07.01-P07.03; P07.14-P07.18

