9.5. Data sources

The Optum EHR with Integrated Claims dataset from the US contains electronic health records data with prescriptions, diagnoses, and provider information as well as practice management data and claims information for deterministically-matched patients. The population of the dataset is made up of commercial health plan members and Medicare Advantage members, across all 50 states. The database currently encompasses the claims and EHR data of more than 95 million patients with approximately 1.9 million patients aged less than 2 years from 01 January 2007 through 31 December 2020. This dataset contains a combination of structured data (e.g. diagnoses, procedures, prescriptions) and information from unstructured data (e.g. drug rationale, provider notes) from the electronic health record and corresponding claims information for those instances. The claims are verified,

adjudicated, and adjusted by the relevant insurer, and de-identified by Optum prior to providing access to the database. Patients are only included in the database if they had both medical and prescription drug coverage, as well as the EHR information. Information is processed, normalized, and standardized across the continuum of care from both acute inpatient stays and outpatient visits. Optum® data elements include demographics, medications prescribed and administered, immunizations, allergies, lab results (including microbiology), vital signs and other observable measurements, clinical and inpatient stay administrative data and coded diagnoses and procedures.¹

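### Criterion 1 admits any IV pantoprazole administration, but section 9.4.1 and Table 2 look for it in inpatient codes with one labeler's NDCs plus two substance-level HCPCS codes, so doses can be missed and index dates set late

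*Protocol*

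**What the plan says.** Criterion 1 in section 9.3.1 asks for "At least one administration of IV pantoprazole during the study period from January 1, 2007 to December 31, 2020". It names no manufacturer and no care setting, and neither do the title or the objectives in section 8. The abstract fixes time zero: "The date of first administration of IV pantoprazole will be defined as the index date". Section 9.4.1 adds: "Only the first treatment episode during the study period will be of interest".

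Ascertainment is narrower. Section 9.4.1 says exposure will be "identified from inpatient procedure and drug codes including any of the following NDC and HCPCS codes shown in Table 2", and the abstract agrees on inpatient codes. Table 2 then lists:
- 12 NDCs, all beginning 0008;
- HCPCS S0164, described as "Injection pantoprazole sodium, 40 mg";
- HCPCS C9113, described as "Injection, pantoprazole sodium, per vial".

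Section 9.2 describes the source as holding insurance claims, "inpatient electronic health records, as well as outpatient EHR enabling capture of exposure to IV pantoprazole in the study population of interest". Section 9.5 lists "medications prescribed and administered" among the data elements. Outcomes, in section 9.4.2, are taken from inpatient or outpatient records.

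**The concern.** The study estimates incidence rates in treated children, and almost every quantity in it is timed from the first and last recorded dose: the index date, the baseline window, the removal of children with a history of the outcome, treatment duration and the end of follow-up. If the code list sees only part of the exposure that criterion 1 describes, two things can go wrong. Children whose doses are all uncaptured never enter. Children with a mix of captured and uncaptured doses enter with wrong dates.

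The second is the more serious for a safety study, because events shortly after the true first dose are the ones at risk of being dropped. Section 9.10 discusses misclassified outcomes and misclassified GERD or EE status, but not missed exposure.

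**Working it through.** **1. What the code list identifies.** All 12 NDCs in Table 2 share the prefix 0008. Table 4 labels the 0008-0923 codes as Protonix and gives esomeprazole, lansoprazole and rabeprazole other prefixes (00186, 64764, 62856). The NDC route is therefore specific to one labeler. The HCPCS descriptions name the substance alone, so that route is open to any labeler.

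| Possible meaning of exposure | NDC arm | HCPCS arm |
|---|---|---|
| The substance, IV (criterion 1) | too narrow | fits |
| The named product, Protonix | fits | too wide |

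Neither meaning fits the whole list. Whether a dose under another labeler's NDC counts depends on whether the hospital also recorded a HCPCS code.

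**2. Setting.** Criterion 1 has no setting limit. Section 9.2 says the source, outpatient EHR included, can show exposure. Section 9.4.1 and the abstract use inpatient codes.

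**3. What an uncaptured dose does under the protocol's rules.** The examples are hypothetical.
- *Index date and history (section 9.8).* Suppose the day 1 dose is uncaptured, an event occurs on day 2 and the first captured dose is on day 3. The index is day 3, the event on day 2 becomes history, and the child leaves both numerator and person-time for that outcome.
- *Duration (section 9.4.3.3).* Duration = last date − first date + 1 − days without a recorded infusion. For infusions on days 1 to 4 this gives 4 − 1 + 1 − 0 = 4, so the child is in the ≥4-day stratum. If day 2 is uncaptured it gives 4 − 1 + 1 − 1 = 3, and the child moves to the <4-day stratum.
- *End of follow-up (section 9.8).* If day 4 is uncaptured, the 90-day limit runs from day 3 and ends on day 93 instead of day 94. A longer uncaptured tail costs correspondingly more.
- *Re-exposure (section 9.8).* If a later separate infusion is uncaptured, follow-up is not censored there as planned.

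**4. Size.** The only figures in the protocol that depend on the number captured are in Table 5. It uses the Wilson interval, [p + z²/(2n) ± z√(p(1−p)/n + z²/(4n²))] / (1 + z²/n), with z = 1.96. With p = rounded events/n, all 12 rows reproduce to four decimals. For 75/7,489 it gives 0.0080 to 0.0125, and for 67/6,657 it gives 0.0079 to 0.0128. Table 5 contains no arithmetic error.

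The share of doses or children missed is not in the documents. As an illustration only, assume that 7,489 and 6,657 are all the treated children and that Table 2 finds a fraction of them. The 95% intervals at p = 0.01 (unrounded) are then:

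| Captured | Cohort 1 n | Interval | Cohort 2 n | Interval |
|---|---|---|---|---|
| 100% | 7,489 | 0.0080–0.0125 | 6,657 | 0.0079–0.0127 |
| 90% | 6,740 | 0.0079–0.0127 | 5,991 | 0.0078–0.0129 |
| 70% | 5,242 | 0.0076–0.0131 | 4,660 | 0.0075–0.0133 |
| 50% | 3,744 | 0.0073–0.0137 | 3,328 | 0.0071–0.0140 |
| 30% | 2,247 | 0.0066–0.0150 | 1,997 | 0.0065–0.0154 |

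Even at 50% capture the cohort 1 interval widens only from 0.0045 to 0.0064. Precision is the lesser issue; selection and misdated index dates matter more, and these cannot be computed from the documents.

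**The case against.** The only medicinal product named is Protonix, and the study answers a requirement tied to that product's application, so a sponsor-only NDC list may be deliberate. That is possible, but the title, objectives and criterion 1 do not say it, and the substance-level HCPCS codes would then not belong.

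The word introducing Table 2 in section 9.4.1 could make the list open-ended. But no other code is given, and section 9.9 says cohort measures are built from the codes in the protocol, which is to be strictly followed. In practice Table 2 is the working list.

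Section 9.2 describes what the source can show and is not an ascertainment rule. This stands: a reader might infer that section 9.2 commits the study to outpatient exposure and is flatly contradicted by section 9.4.1, and that goes too far. What remains is an inpatient rule narrower than the eligibility criterion it puts into operation, with no reason given.

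A reader might also infer that treated children are in fact missed. The documents do not show this. They do not say that another labeler's IV pantoprazole was used, or that any child was dosed outside inpatient care, and the HCPCS codes can recover some other-labeler doses.

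Nor can a share of uncaptured doses be read as the same share of children lost. A child is lost only if every dose is uncaptured. If recording is all-or-none by hospital, children drop out but index dates are right. If it is mixed, fewer drop out but more dates are wrong.

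**Conclusion.** The point holds as an inconsistency in a rule that the protocol itself fixes. The code list matches neither the product nor the substance, and the setting used for ascertainment is narrower than criterion 1. Doses falling outside the list can be missed, with the effects on index date, history, duration stratum and follow-up shown above.

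The size is unknown, because it depends on how many doses were recorded only under other labelers' NDCs or only outside inpatient records. It is tempting to conclude that the rates will be too low. Dropping early events as history does push early-event rates down. But ending follow-up early removes events and person-time together, so the net direction is uncertain. The change should be made before the cohorts are built, because it is cheap and the affected rules drive every rate.

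**What to change.** Make Table 2 and section 9.4.1 match criterion 1: list all IV pantoprazole NDCs whatever the labeler, keep the two HCPCS codes, take administrations from every setting the source holds, and state that the list is complete.

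If a narrower exposure is intended, restate the objectives and criterion 1 instead. For the named product only, say so and drop the HCPCS codes that are not product-specific. For inpatient use only, say so and give the reason.

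In either case, rerun the feasibility counts of 7,489 and 6,657 on the final list (section 9.6 does not say which codes produced them), update Table 5 if they change, and add missed exposure to the limitations in section 9.10.

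The cost is a longer code list, one rerun count and a short amendment. Section 9.5 suggests that the existing source can support this, although the protocol does not describe the fields that would be searched.

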9.4.2. Outcomes of interest

The outcomes of interest are listed in Table 3 below. These outcomes were based on the Investigator's Brochure (version 4.0 June 2021) and expert clinical judgment. The first occurrence of each outcome is defined based on the presence of at least one ICD-9-CM or ICD-10-CM diagnosis code identified in the inpatient or outpatient setting during the follow-up period.

Outcome of interest	Operationalization: ICD-10-CM code	Operationalization: ICD-9-CM code
Agranulocytosis	D70.2 Other drug-induced agranulocytosis D70.1 Agranulocytosis secondary to cancer chemotherapy	288.03 Drug induced neutropenia
Thrombocytopenia	D69.3 Immune thrombocytopenic purpura D69.59 Other secondary thrombocytopenia D69.6 Thrombocytopenia, unspecified D69.41 Evans syndrome D69.49 Other primary thrombocytopenia	287.31 Immune thrombocytopenic purpura 287.49 Other secondary thrombocytopenia 287.5 Thrombocytopenia, unspecified 287.30 Primary thrombocytopenia, unspecified 287.32 Evans syndrome 287.39 Other primary thrombocytopenia
Leukopenia	D72.810 Lymphocytopenia D72.818 Other decreased white blood cell count D72.819 Decreased white blood cell count, unspecified D70.8 Other neutropenia D70.9 Neutropenia, unspecified D70.0 Congenital agranulocytosis	288.51 Lymphocytopenia 288.59 Other decreased white blood cell count 288.50 Leukocytopenia, unspecified 288.09 Other neutropenia 288.00 Neutropenia, unspecified
Pancytopenia	D61.811 Other drug-induced pancytopenia	284.12 Other drug-induced pancytopenia
	D61.818 Other pancytopenia	284.19 Other pancytopenia

Hypersensitivity (including anaphylactic reactions and anaphylactic shock)	K52.2x Allergic and dietetic gastroenteritis and colitis M31.0 Hypersensitivity angiitis T78.2x Anaphylactic shock, unspecified T78.4x Other and unspecified allergy M36.4x Arthropathy in hypersensitivity reactions classified elsewhere	558.3 Allergic gastroenteritis and colitis 446.20 Hypersensitivity angiitis, unspecified 446.21 Goodpasture's syndrome 446.29 Other specified hypersensitivity angiitis 995.0 Other anaphylactic reaction, Not elsewhere classified (NEC) 995.3 Allergy, unspecified, NEC 713.6 Arthropathy associated with hypersensitivity reaction
Hyperlipidemia	E78.49 Other hyperlipidemia E78.5 Hyperlipidemia, unspecified	272.4 Other and unspecified hyperlipidemia
Hypertriglyceride mia	E78.1 Pure hyperglyceridemia	272.1 Pure hyperglyceridemia
Hyponatremia	E87.1 Hypo-osmolality and hyponatremia	276.1 Hypo-osmolality and/or hyponatremia
hypomagnesemia	E83.42 Hypomagnesemia	275.2 Disorders of magnesium metabolism
Hypocalcaemia	E83.51 Hypocalcemia	275.41 Hypocalcemia
Hypokalemia	E87.6 Hypokalemia	276.8 Hypopotassemia
Diarrhea	R19.7 Diarrhea, unspecified	787.91 Diarrhea
Vomiting	R11.10 unspecified R11.11 without nausea	536.2 Persistent vomiting 078.82 Epidemic vomiting syndrome

version 2.0, 10 Fe	toruary 2022	
	R11.12 Projectile vomiting R11.13 Vomiting of fecal matter R11.2 Nausea with vomiting, unspecified	787.03 Vomiting alone 569.87 Vomiting of fecal matter 787.01 Nausea with vomiting
Abdominal distension	R14.0 Abdominal distension (gaseous)	787.3 Flatulence, eructation, and gas pain
Hepatobiliary injury	K71x Toxic liver disease K72x Hepatic failure, not elsewhere classified K72.00 Acute and subacute hepatic failure without coma K72.01 Acute and subacute hepatic failure with coma K72.10 Chronic hepatic failure without coma K72.11 Chronic hepatic failure with coma K72.90 Hepatic failure, unspecified without coma K72.91 Hepatic failure, unspecified with coma K73x Chronic hepatitis K73.0 Chronic persistent hepatitis, not elsewhere classified K73.1 Chronic lobular hepatitis, not elsewhere classified K73.2 Chronic active hepatitis, not elsewhere classified K73.8 Other chronic hepatitis, not elsewhere classified K73.9 Chronic hepatitis, unspecified K73.9 Chronic hepatitis, unspecified K74 Fibrosis and cirrhosis of the liver	573.3 Hepatitis, unspecified 570 Acute and subacute necrosis of liver 572.2 Hepatic encephalopathy. 572.8 Other sequelae of chronic liver disease 571.41 Chronic persistent hepatitis 571.49 Other chronic hepatitis 571.5 Cirrhosis of liver without mention of alcohol 571.9 Unspecified chronic liver disease without mention of alcohol 571.6 Biliary cirrhosis 571.42 Autoimmune hepatitis 571.8 Other chronic nonalcoholic liver disease 573 Other disorders of the liver 573.0 Chronic passive congestion of liver 573.8 Other specified disorders of liver 573.4 Hepatic infarction 572.3 Portal hypertension 572.4 Hepatorenal syndrome 573.5 Hepatopulmonary syndrome 573.9 Unspecified disorder of liver 782.4 Jaundice, unspecified, not of newborn

K74.00 Hepatic fibrosis, unspecified K74.01 Hepatic fibrosis, early fibrosis K74.02 Hepatic fibrosis, advanced fibrosis K74.1 Hepatic sclerosis K74.3 Primary biliary cirrhosis K74.4 Secondary biliary cirrhosis K74.5 Biliary cirrhosis, unspecified K74.60 Unspecified cirrhosis of liver K74.69 Other cirrhosis of liver K75x Other inflammatory liver diseases K75.2 Nonspecific reactive hepatitis K75.3 Granulomatous hepatitis, not elsewhere classified K75.4 Autoimmune hepatitis K75.81 Nonalcoholic steatohepatitis (NASH) K75.89 Other specified inflammatory liver diseases K75.9 Inflammatory liver disease, unspecified K76x Other diseases of the liver K76.0 Fatty (change of) liver, not elsewhere classified K76.1 Chronic passive congestion of liver K76.2 Central hemorrhagic necrosis of liver K76.3 Infarction of liver K76.4 Peliosis hepatis K76.5 Hepatic venoocclusive disease

	10 1 cordary 2022	
	K76.6 Portal hypertension K76.7 Hepatorenal syndrome K76.81 Hepatopulmonary syndrome K76.89 Other specified diseases of liver K76.9 Liver disease, unspecified K77 Liver disorders in diseases classified elsewhere K71.6 Toxic liver disease with hepatitis, not elsewhere classified K71.2 Toxic liver disease with acute hepatitis K71.3 Toxic liver disease with chronic persistent hepatitis K71.4 Toxic liver disease with chronic lobular hepatitis K71.50 Toxic liver disease with chronic active hepatitis without ascites K71.51 Toxic liver disease with chronic active hepatitis with ascites R17 Unspecified jaundice	
Urticaria	L50.0 Allergic urticaria L50.1 Idiopathic urticaria L50.8 Other urticaria L50.9 Urticaria, unspecified	708.0 Allergic urticaria 708.1 Idiopathic urticaria 708.8 Other specified urticaria 708.9 Urticaria, unspecified
Angioedema	T78.3XXA Angioneurotic edema initial encounter T78.3XXD Angioneurotic edema subsequent encounter T78.3XXS Angioneurotic edema sequela	995.1 Angioneurotic edema, not elsewhere classified

10 February 2022

2.0,

Version

version 2.0, 101	editiary 2022	Ī
Stevens- Johnson syndrome	L51.1 Stevens-Johnson syndrome L51.3 Stevens-Johnson syndrome -toxic epidermal necrolysis overlap syndrome	695.13 Stevens-Johnson syndrome 695.14 Stevens-Johnson syndrome- toxic epidermal necrolysis overlap syndrome
Lyell syndrome	L51.2 Toxic epidermal necrolysis [Lyell]	695.15 Toxic epidermal necrolysis

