The cut-off of birth weight less than 2.36 kilograms is defined based on a birth weight that is less than third percentile weight for males at birth obtained from Centers for Disease Control and Prevention (CDC) infant weight-for-age charts (available at URL: https://www.cdc.gov/growthcharts/html charts/wtageinf.htm). It is reasonable to assume that infants with birth weight less than 2.36 kilograms are most likely born preterm.

9.3.3. **Subgroups**

Within each cohort (ie, Cohort 1 and 2), 3 subgroups will be identified as follows:

- (1) Patients who have a diagnosis of GERD with EE: defined based on the presence of at least one of the ICD-9-CM or ICD-10-CM codes as shown in Table 1 and the presence of an additional ICD-9-CM or ICD-10-CM code for ulcer of the esophagus during the baseline period or on the index date, as shown in Table 1.
- (2) Patients who have a diagnosis of GERD without EE: defined based on the presence of at least one of the ICD-9-CM or ICD-10-CM codes and no ICD-9-CM or ICD-10-CM code for ulcer of esophagus during the baseline period or on the index date, as shown in Table 1.
- (3) Patients without a diagnosis of GERD or EE: defined as patients who do not have any of the ICD-9-CM or ICD-10-CM codes as shown in Table 1 during the baseline period or on the index date.

ICD-9-CM codes will be used to identify the subgroups prior to October 2015, after which ICD-10-CM codes will be used. No validated algorithm for GERD with or without EE were found to be available via literature review, therefore, a combination of clinical input, and the available codes identified in the literature will be used.² Additionally, there is no explicit ICD-9-CM code for GERD with/without esophagitis. Therefore, based on a cross-sectional study that examined the validity of diagnosis codes of benign upper gastrointestinal disorders using electronic patient records², and an online conversion tool maintained by the Center for Medicare Services and the Centers for Disease Control and Prevention (available at URL: https://icd.codes/convert/icd10-to-icd9-cm), the subgroups of GERD with or without EE will be determined using the operational definitions shown in Table 1:

Table 1. Operationalization of subgroups

Subgroup	ICD-10- CM Code	Description of ICD- 10-CM code	ICD-9- CM Code	Description of ICD-9- CM code

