More sensitive algorithms will be employed (i.e. algorithms based only on diagnostic codes, rather than more specific algorithms employing procedure and treatment codes in addition to diagnostic codes) for capturing outcomes to ensure safety events of interest are not missed.

However, the limitation of this approach is that, the incidence of some outcomes may be overestimated. Infants with a diagnosis of GERD with EE may be misclassified as those without EE. This is because a confirmed diagnosis of GERD with EE may not be available in infants due to reluctance of healthcare professionals to seek a confirmation via endoscopy. Also, those with a presumptive diagnosis of EE may be classified into the subset of infants with GERD alone. Prior to October 2015, ICD-9-CM codes were exclusively used to identify eligible patients, and GERD is not explicitly captured under this coding schema. ICD-10-CM codes provide additional granularity, but a validated code for erosive esophagitis and GERD is not available, nor well-established or validated in the literature. However, including patients identified using both coding schemes is important to increase sample size of this small population of pediatric patients with a rare condition and exposure. To examine the impact of different coding systems, a sensitivity analysis stratified by those patients identified via ICD-9-CM codes versus ICD-10-CM codes, respectively is planned. The counts of the top 25 most common conditions occurring within 30 days prior to or on the index date through 90 days of the last treatment with IV pantoprazole may include prevalent/comorbid conditions and not just conditions emerging following IV pantoprazole administration. This will however help generate hypotheses about unsuspected safety events in this patient population. Furthermore, a pre-planned sensitivity analysis stratifying by each code type will be performed for the analysis to understand if significant heterogeneity exists in this patient population with respect to the incidence of these outcomes following administration of IV pantoprazole. Finally, the study results may not be generalizable to infants aged 1 month to <1 year and patients aged 1 to <2 years outside of the commercially insured population.

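### The ICD-10-CM list for the hypersensitivity outcome has no code for drug-attributed anaphylaxis, so such reactions may go uncounted from October 2015

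*Protocol*

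**What the plan says.** Section 9.4.2, Table 3, names the outcome "Hypersensitivity (including anaphylactic reactions and anaphylactic shock". Its ICD-10-CM column has five entries: K52.2x, M31.0, T78.2x, T78.4x and M36.4x. The one that concerns anaphylaxis is "T78.2x Anaphylactic shock, unspecified". The nearest neighbour is "T78.4x Other and unspecified allergy", which is worded as allergy. In the ICD-9-CM column the anaphylaxis entry is "995.0 Other anaphylactic reaction, Not elsewhere classified (NEC".

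The counting rule in the same section is the "presence of at least one ICD-9-CM or ICD-10-CM diagnosis code identified in the inpatient or outpatient setting during the follow-up period". Section 9.9 says that measures are built from the codes in the protocol and that the protocol will be strictly followed. Sections 9.3.1 and 9.8 remove children with a history of the outcome before the index date, so the same list also decides who is at risk.

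On timing, Section 9.2 states: "The study period will be defined from 01 January 2007 to 31 December 2020". Section 9.3.3 states: "ICD-9-CM codes will be used to identify the subgroups prior to October 2015, after which ICD-10-CM codes will be used".

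**The concern.** The drug is given intravenously, and the row label undertakes to capture anaphylactic reactions. By its own descriptor, the one ICD-10-CM anaphylaxis entry is for shock with no specified cause. A reaction that the treating clinician puts down to a drug appears to fall outside it, and no other entry in the row takes it in.

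Two things are at stake. The hypersensitivity incidence rate could be too low from October 2015 onward. The two coding eras could also differ because their lists differ. Table 6 plans incidence rates stratified by ICD-9-CM versus ICD-10-CM and compares them to look for heterogeneity between patients, so a gap produced by the code list could be mistaken for a difference in patients.

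**Working it through.** The plan gives no figure on this point, so there is none to reproduce. The check is a reading of the code list, followed by an illustration of scale.

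**1. Label against codes (ICD-10-CM, hypersensitivity row).**
- K52.2x: allergic or dietetic gut inflammation; not anaphylaxis.
- M31.0: hypersensitivity angiitis; not anaphylaxis.
- T78.2x: anaphylactic shock, cause unspecified.
- T78.4x: other or unspecified allergy; not worded as anaphylaxis.
- M36.4x: joint disease in hypersensitivity; not anaphylaxis.

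One of five entries concerns anaphylaxis, and none is drug-attributed.

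**2. Rest of Table 3.** No other row lists a drug-attributed anaphylaxis code. The closest is T80.90, an unspecified infusion complication, which counts toward injection site thrombophlebitis and not toward hypersensitivity.

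**3. Comparison with other rows.** Drug-induced codes are used for agranulocytosis (D70.2), pancytopenia (D61.811), interstitial nephritis (N14.1) and photosensitivity (L56.0). Their absence here does not follow a rule applied throughout the table.

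**4. Outside assumption.** ICD-10-CM is assumed to file an anaphylactic reaction to a correctly administered drug under its own code, T88.6x, and not under T78.2x. The protocol does not print this code. Given the assumption and the counting rule, a child with that code and no other listed code is not an event. The child also keeps contributing person-time. A child with that code before the index date is not removed as a prevalent case.

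**5. Share of the calendar.** From 1 October 2015 to 31 December 2020 is 1,919 days. From 1 January 2007 to 31 December 2020 is 5,114 days. 1,919 / 5,114 = 37.5%. Section 9.3.3 gives the switch date for subgroups; its use for outcomes is an inference from the same change of coding system. The number of children by calendar year is not given, so the share of person-time may differ from 37.5%.

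**6. Illustration only.** Let m be the unknown share of true composite hypersensitivity events in the ICD-10 era whose only relevant code is the drug-attributed one. Capture in that era is 1 − m. If events are spread evenly over the calendar and the ICD-9 list is complete, pooled capture is 1 − 0.375m.

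| m (assumed) | Captured, ICD-10 era | Captured, pooled |
|---|---|---|
| 0.10 | 90% | 1 − 0.375 × 0.10 = 96% |
| 0.25 | 75% | 1 − 0.375 × 0.25 = 91% |
| 0.50 | 50% | 1 − 0.375 × 0.50 = 81% |

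With equal true rates, the ICD-10 to ICD-9 rate ratio in the stratified analysis would be close to 1 − m. The documents give no basis for choosing m.

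**The case against.** **The consequence depends on a coding convention that the protocol does not state.** This is correct, and the point is therefore conditional. The mismatch between the row label and the ICD-10-CM entries is visible without that convention.

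**The ICD-9-CM entry is residual wording too and is not drug-attributed.** This also stands. A reader might infer that the gap is confined to the ICD-10 era, but the documents do not establish that. 995.0 is worded as a reaction and is not limited to shock, but whether it covers the same concept has to be checked.

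**The study is descriptive.** A reader might see it as intended to detect anaphylaxis caused by the drug. Section 9.1 sets no comparator and no hypotheses, and Section 11 says product and event cannot be linked for an individual. The study counts events after exposure, whatever their cause. Nor is a separate anaphylaxis rate planned: the reported quantity is the composite. A confidence limit for zero anaphylaxis events would therefore describe no planned output, and none is used here.

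**Section 9.10 is not contradicted.** A reader might set the list against the statement that sensitive algorithms are used "for capturing outcomes to ensure safety events of interest are not missed". In context, that sentence contrasts diagnosis-only algorithms with ones that also require procedure or treatment codes. It does not say that every list is complete, and the same section acknowledges outcome misclassification.

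**Some children would be caught by other codes.** A child who also receives T78.2x or T78.4x is counted in this row. Urticaria, angioedema and infusion complications are captured, but under other outcomes, so they do not restore the hypersensitivity count. The planned ICD-9/ICD-10 stratification might show a difference between eras; it would neither recover missed events nor explain the cause.

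**Conclusion.** The point holds in conditional form. The ICD-10-CM list does not visibly deliver what the row label promises: anaphylaxis enters only through shock of unspecified cause, and no entry covers a reaction attributed to a drug. If the code-book check confirms a separate code, the composite hypersensitivity rate is underestimated in the ICD-10 era, about 37.5% of the study calendar, and the two eras may differ through coding alone. The undercount affects only children with no other code in the row, and its size cannot be computed from the documents; the table of assumed shares shows the form of the effect and is not an estimate. The matter belongs in the protocol because the list is fixed there, and Amendment 1 already corrected code lists in Table 3. It merits correction but does not undermine the study as a whole.

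**What to change.** In Table 3, after a code-book check, add the code(s) for an anaphylactic reaction to a correctly administered drug (T88.6x, if confirmed) to the ICD-10-CM hypersensitivity row. Confirm in the same check that 995.0 covers this concept in ICD-9-CM, so that the two columns match. Use the revised list both for the outcome and for the outcome-history exclusion in Sections 9.3.1 and 9.8. If the check shows that T78.2x already includes drug-attributed reactions, state this in Table 3 and add nothing.

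The cost is one amended row and a rerun of one outcome in both cohorts, including the two sensitivity analyses. No new data are needed. A small downside is that reactions to other drugs given in the same period will also be counted. Section 9.10 already accepts possible overestimation for some outcomes as a consequence of diagnosis-only algorithms.
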